11. STATISTICAL CONSIDERATIONS

11.1 General Considerations

Statistical analysis of this study will be the responsibility of Enanta Pharmaceuticals, Inc. or its designee. Details of the statistical analysis methods will be described in the statistical analysis plan (SAP) document.

Continuous endpoints will be summarized using n, mean, standard deviation, median, 25th quartile, 75th quartile, minimum, and maximum values. Categorical endpoints will be summarized by the number of subjects meeting the endpoint and the percentage of subjects out of the appropriate population. The denominator will be displayed when needed. Statistical inference will be performed as appropriate. Inferential testing will be conducted using a two-sided alpha of 0.05, unless stated otherwise.

Any change to the data analysis methods described in the protocol will require an amendment if it changes a principal feature of the protocol. Any other change to the data analysis methods described in the protocol, and the justification for making the change, will be described in the clinical study report or SAP. Changes may only be made in the SAP prior to unblinding.

11.2 Sample Size Considerations

Using a ratio of 1:1, a sample size of 27 subjects per treatment group (54 subjects total) provides 80% power to detect a treatment reduction in TSS AUC of at least 55% from placebo (assuming TSS AUC from the previous Phase 2a clinical challenge study to: mean [standard deviation]) of placebo: 500 [450] and EDP-938: 225 [200]) using a t-test with unequal variance. Assuming a 20% dropout rate, approximately 35 subjects per treatment group (approximately 70 subjects total) are needed.

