23. History of or currently experiencing a medical condition or any other finding (including laboratory test results) that, in the opinion of the Investigator, might confound the results of the study; pose an additional risk in administering study drug to the subject; could prevent, limit, or confound the protocol-specified assessments; or deems the subject unsuitable for the study.

Additional Exclusion Criteria for Subjects With Asthma

24. Subjects must not have experienced a severe asthma exacerbation (defined as worsening asthma that requires treatment with oral corticosteroids for 3 or more days, or emergency room attendance) or deterioration in asthma requiring an increase in asthma treatment for at least 6 weeks prior to Screening.
25. Subject is receiving more than two maintenance asthma therapies or theophylline preparations for asthma treatment.
26. Pulse oximetry reading of <90% oxygen saturation measured at rest at Screening.

Additional Exclusion Criteria for Subjects With COPD

27. Receipt of theophylline, roflumilast, maintenance oral corticosteroids, or long-term oxygen therapy (defined as prescribed for 12 or more hours per day).
28. Exacerbation of COPD requiring treatment with systemic corticosteroids and/or antibiotics, or emergency room attendance or hospitalization within 6 weeks prior to Screening.
29. More than three COPD exacerbations with the past 12 months.
30. Pulse oximetry reading of <90% oxygen saturation measured at rest at Screening.

Subject Withdrawal: Subjects may be discontinued from the study at any time if the subject, Investigator, or Sponsor determines that it is not in the best interest of the subject to continue participation. Reasons for discontinuation include the following:

- AE
- Lack of efficacy
- Lost to follow-up
- Withdrawal by subject
- Protocol deviation (including noncompliance with study drug or study procedures)
- Pregnancy
- Study terminated by the Sponsor
- Other

Statistical Methods: Detailed statistical analysis will be outlined in the statistical analysis plan, which will be developed and finalized prior to database lock.

Sample Size Considerations: Using a ratio of 1:1, a sample size of 27 subjects per treatment group (54 subjects total) provides 80% power to detect a treatment reduction in TSS AUC of at least 55% from placebo (assuming TSS AUC from the previous Phase 2a clinical challenge study to: mean [standard deviation] of placebo: 500 [450] and EDP-938: 225 [200]) using a t-test with

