4.2.1 Justification of Study Design, Endpoints, and Subject Population

Despite the significant medical need, there is no vaccine or highly effective treatment currently available for RSV. At present, there are only two agents approved for the prevention or treatment of RSV lower respiratory tract disease, a prophylactic agent (palivizumab) and a therapeutic agent (aerosolized ribavirin); each having indications for use that are limited to the pediatric population. Analyses performed subsequent to the approval of aerosolized ribavirin suggest that it failed to impart any clinically significant benefits (*Randolph and Wang, 1996*). Consequently, physicians have no safe and highly effective treatment for RSV infection. This is an issue of significant concern for those providing medical care for patients at risk of severe RSV disease, including the elderly, those with chronic lung and/or heart diseases, immunosuppressed individuals, and pediatric patients. In these populations, RSV infection may be associated with significant morbidity and even mortality.

This Phase 2b study aims to evaluate the efficacy and safety of EDP-938 in an adult population with early detection of RSV infection as well as early initiation of EDP-938. In order to more fully investigate the efficacy of EDP-938, and noting the lack of a highly effective RSV therapy, a double-blind, placebo-controlled study design was selected, where subjects will be randomized to receive either 800 mg of EDP-938 or placebo in a 1:1 fashion. The study endpoints include efficacy and safety assessments. The primary endpoint is based on the subject's twice daily assessment of defined, RSV-related, clinical symptoms over the course of the 14-day study. These data will enable the calculation of the AUC for the TSS as was used in the Phase 2a EDP 938-101 study. The antiviral efficacy will be assessed as the AUC for RSV RNA quantitation by nasopharyngeal swab over the course of the 14-day study. The RSV RNA AUC assessment was similarly employed in the Phase 2a EDP 938-101 study. Safety and PK assessments will also be summarized in relation to study treatment group.

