4.2.2 Justification of EDP-938 Dose

EDP-938 has been comprehensively characterized in preclinical and clinical studies.

[REDACTED]

[REDACTED]

Study EDP 938-101 is an ongoing Phase 2a study evaluating the safety, PK, and antiviral activity of multiple doses of orally administered EDP-938 against RSV infection in the healthy volunteer virus-challenge model (see [Section 1.5](#)). The study is composed of two parts and final data analyses are available for Part 1, in which a total of 115 subjects were randomized (1 subject

randomized was not dosed) to receive placebo (n=38), 600 mg once daily (n=39), or a single 500 mg LD followed by 300 mg twice daily (n=38) for 5 days.

Data from Part 1 of the EDP 938-101 study demonstrated proof-of-concept in adults inoculated with RSV. The primary and key secondary efficacy endpoints were achieved with high statistical significance at both dose levels, 600 mg once daily and a 500 mg LD followed by 300 mg twice daily. Both EDP-938 treatment regimens demonstrated robustly lower RSV RNA AUC values compared to placebo ($p < 0.001$) with no significant difference between the once daily and twice daily treatment groups. Additional study findings were as follows:

- Both EDP-938 treatment regimens demonstrated robustly lower 10-point TSS AUC values compared to placebo ($p < 0.001$) with no significant difference between once daily and twice daily treatment groups.
- Both EDP-938 regimens were observed to be generally safe and well tolerated with no SAEs, severe AEs, or discontinuations of EDP-938 due to AEs (see [Section 1.5](#)).

The mean EDP-938 trough concentrations (C_{trough}) were maintained at 22- to 42-fold above the *in vitro* 90% maximal effective concentration (EC_{90}) for RSV M37. The mean (coefficient of variation) total daily EDP-938 AUC after the last dose was approximately 24,700 (38.4) ng·hr/mL and 26,300 (29.0) ng·hr/mL for the 600 mg once daily group and the 500 mg LD followed by 300 mg twice daily group, respectively. The systemic exposures in this study were generally comparable to those observed in Study EDP-938-001 at similar doses.

[REDACTED]

The dose selected for the present Phase 2b EDP 938-102 study is 800 mg of EDP-938 (or placebo) administered as a tablet formulation once daily for 5 days.

[REDACTED]

 These systemic EDP-938 exposures are expected to be generally safe and efficacious.

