8.3.8 Respiratory Syncytial Virus Symptom Diary

At Screening and at timepoints indicated in the SoA ([Appendix 1](#)), subjects will assess the severity of RSV-related signs and symptoms and self-complete the 13-point RSV symptom diary. The 13-item diary will consist of grading symptoms on a scale of 0 to 3, where Grade 0 is absence, Grade 1 is just noticeable, Grade 2 is bothersome but does not prevent participation in activities, and Grade 3 is bothersome and interferes with activities. The 13 RSV symptoms assessed will comprise nasal discharge, nasal congestion, malaise/tiredness, headache, sinus congestion, sneezing, sore throat, hoarseness, cough, shortness of breath, respiratory wheeze, earache, and/or symptoms of fever. The RSV symptom diary will be completed twice daily at the same times each day ± 2 hours as an eCOA. In case the subject is unable to complete the RSV symptom diary assessment for technical reasons, the subject will also be provided with a paper diary(ies) as a back-up. If a subject plans to take acetaminophen within 2 hours of the scheduled RSV symptom diary completion, then the RSV symptom diary should be completed immediately before the subject takes acetaminophen or 4 hours after taking acetaminophen.

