The TSS AUC from Day 1 through Day 14 will be calculated using the trapezoid rule (*Matthews et al., 1990*). The AUC will require at least 2 non-missing calculated total symptom scores. Missing total symptom score data will be reviewed for potential impact, and any decisions to include subjects that fail these criteria above will be documented. The AUC will be calculated based on available individual assessments of TSS collected twice per day from Day 1 through Day 14, and the actual date/time of each assessment will be used for the calculation. For the baseline TSS, the actual time is set as 0. For each assessment post first dose, the actual time in days is computed as difference between the date/time of the assessment and the date/time of the first dose. The AUC is also standardized for 14 days by multiplying  $14/t_{last}$  where  $t_{last}$  is the actual time in days of the last available assessment. Additionally, the AUC from Day 1 through Day 3, the AUC from Day 1 through Day 5, and the AUC from Day 1 through Day 9 will be also derived and standardized similarly as for AUC from Day 1 through Day 14.

The AUC TSS from Day 1 through Day 14 will be compared between EDP-938 and placebo using an analysis of covariance (ANCOVA) model with treatment group, asthma/COPD status (present or absent) as factors and the baseline TSS as a covariate. The analysis will be performed using SAS procedure MIXED. Treatment groups will be compared using a type III sum-of-squares. The least-squares means, standard errors and two-sided 95% confidence intervals (CI) will be presented for individual groups and the difference between groups. The same ANCOVA analysis will be performed for the TSS AUC from Day 1 through Day 3, from Day 1 through Day 5 and from Day 1 through Day 9.

Descriptive statistics will be displayed for TSS and change from baseline by day and timepoint and also for average daily TSS by day and will include at a minimum the number of non-missing measurements, mean, standard deviation, median, minimum, maximum, and 95% CI for the mean.

Multiple line graphs of TSS will be produced:

- (1) Observed mean TSS  $\pm$  95% confidence interval by days 1-14 and timepoint for each treatment group
- (2) Observed mean TSS (average per day)  $\pm$  95% confidence interval by days 1-14 for each treatment group

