## 5.2 RSV Symptom Diary

The RSV Symptom Diary includes 13 items that assess the severity of RSV-related signs and symptoms. The 13 items are as follows: Nasal discharge, Nasal congestion (stuffy nose), Malaise/tiredness, Headache, Sinus congestion (sinus pressure), Sneezing, Sore throat, Hoarseness, Cough, Shortness of Breath, Respiratory wheeze, Earache, and Symptoms of fever. For each item, severity is rated using a 4-point scale: 0=absent, 1=noticeable, 2=Bothersome but does not interfere with activities, 3=Bothersome and interferes with activities. The total symptom score (TSS) is calculated as the sum of item scores across all 13 items. If *any* of the 13 observed values are missing the total symptom score will not be calculated for that assessment. The TSS ranges from 0 to 39 with higher scores indicating more severe symptoms.

The RSV Symptom Diary will be completed by subjects using a handheld device. Each subject will also be provided with a paper diary(ies) as a back-up, in case the subject is unable to complete the RSV symptom diary assessment for technical reasons. Diaries will be completed twice daily from Day 1 (date of first dose) through Day 14 at the same times each day  $\pm$  2 hours. Subjects are instructed to rate the severity of symptoms experienced in the last 12 hours for the morning diary on Day 1 then the maximum since the last completed diary for the subsequent diaries.

Throughout the study the subject may take acetaminophen for pain and fever relief. The subject should not take other pain relievers such as ibuprofen or naproxen. Each time the subject completes the diary acetaminophen use needs to be recorded. The time of the day the subject takes acetaminophen will be important to document due to the confounding effect on the primary analysis. If a subject plans to take acetaminophen within 2 hours of a scheduled RSV symptom diary completion, then the RSV symptom diary should be completed immediately before the subject takes acetaminophen or 4 hours after taking acetaminophen.

[REDACTED]

[REDACTED]

[REDACTED]

[REDACTED]

[figure not shown]
[REDACTED]

[REDACTED]

[REDACTED]

[REDACTED]

[REDACTED]

[Redacted text block]

[Redacted text block]

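### Does it matter that the Phase 2a planning values behind the sample size carry no unit and cannot be on the SAP's score-day scale?

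*Protocol*

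**What the plan says.** Protocol 11.2 takes its means and SDs from the earlier challenge study: "placebo: 500 [450] and EDP-938: 225 [200]) using a t-test with unequal variance". The Protocol Summary repeats them: "mean [standard deviation] of placebo: 500 [450] and EDP-938: 225 [200". Neither place gives a unit, an AUC window or an item set. The target itself is worded as a reduction of at least 55% from placebo. The stated result is 27 per arm for 80% power, raised to about 35 per arm for 20% dropout.

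The documents describe the score as follows.

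- Protocol 4.2.1, on this trial's diary: "These data will enable the calculation of the AUC for the TSS as was used in the Phase 2a EDP 938-101 study".
- Protocol 4.2.2, on the Phase 2a result: "robustly lower 10-point TSS AUC values compared to placebo".
- Protocol 8.3.8, on this trial's instrument: "self-complete the 13-point RSV symptom diary. The 13-item diary will consist of grading symptoms on a scale of 0 to 3".
- SAP 5.2: "The TSS ranges from 0 to 39 with higher scores indicating more severe symptoms".
- SAP 3.14.1, on the time axis of the AUC: "the actual time in days is computed as difference between the date/time of the assessment and the date/time of the first dose". The AUC is then scaled to 14 days.
- SAP 3.14.1, on reporting of the least-squares means: "two-sided 95% confidence intervals (CI) will be presented for individual groups and the difference between groups".

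**The concern.** A reader who sets the planning values beside the SAP endpoint finds that they do not fit. A placebo mean of 500 would be an average score of 35.7 out of 39 held for 14 days, and an SD of 450 is impossible on that range. This suggests either that the sample size was computed on the wrong scale or that the endpoint changed after planning.

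The instrument adds to the doubt. Protocol 8.3.8 uses 13-point and 13-item for the same diary, so the 10-point score in 4.2.2 reads as ten items. Protocol 4.2.1 nevertheless links the two AUCs without mentioning the difference.

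Two things seem to be at stake. If the scale were wrong, power and sample size might be wrong too. Even if they are right, the planned difference of 275 cannot be placed next to the least-squares mean difference that the SAP will report.

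**Working it through.** **Inputs.** Means 500 and 225, SDs 450 and 200, 27 per arm, unequal-variance t-test and 20% dropout (Protocol 11.2); two-sided alpha 0.05 (Protocol 11.1); score range 0 to 39 (SAP 5.2); time in days, 14-day window (SAP 3.14.1).

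**1. The plan's own figure.**

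- Standard error at 27 per arm: √((450² + 200²)/27) = √(242,500/27) = 94.8.
- Noncentrality: 275/94.8 = 2.90.
- Satterthwaite df: 26 × 242,500²/(202,500² + 40,000²) = 35.9.
- Power from the noncentral t distribution: 80.6%. At 26 per arm it is 79.0%, so 27 is the smallest number that reaches 80%.
- Dropout: 27/0.8 = 33.75, or 34 per arm, against about 35 stated.

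The stated sample size reproduces.

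**2. Can the values be score-days on this trial's endpoint?**

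- Ceiling: 39 × 14 = 546.
- For a quantity bounded by 0 and M with mean m, the largest possible SD is √(m(M − m)).
- Placebo: √(500 × 46) = 151.7, against 450 stated. Impossible.
- EDP-938: √(225 × 321) = 268.7, against 200 stated. Possible alone, but both pairs must share one unit.
- The placebo pair needs a ceiling of at least 500 + 450²/500 = 905.

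So the quoted values are on some other scale.

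**3. Does the unit affect the power?** Multiply all four values by a constant k. The difference and the standard error both scale by k, so the noncentrality stays at 2.90. The df is a ratio of variances, so it stays at 35.9. Each unit below is an assumption, since neither document names one for Phase 2a.

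| Assumed original unit | Placebo, score-days | EDP-938, score-days | Difference | Power at 27 per arm |
|---|---|---|---|---|
| Score-hours (divide by 24) | 20.8 [18.75] | 9.4 [8.3] | 11.5 | 80.6% |
| Half-day readings (divide by 2) | 250 [225] | 112.5 [100] | 137.5 | 80.6% |

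Both rows fit within 0 to 546: the placebo SD limits are 105 and 272. A purely proportional move from 10 to 13 items (multiply by 1.3) also leaves 80.6%.

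**4. What would change the power?** A different relative effect would. With SDs held at 450 and 200 and 27 per arm, illustrative reductions of 45%, 35% and 25% give 64%, 44% and 25% power. This sensitivity is the same in every unit.

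**The case for a change.** The strongest case for a change runs as follows. The unit cancels only if the relative effect and the coefficients of variation (450/500 = 0.90 and 200/225 = 0.89) carry over from a 10-point score in inoculated volunteers to a 13-item score in symptomatic outpatients, and 11.2 does not spell that out. Without a unit, 275 might be 11.5 or 137.5 score-days, so nobody can say whether the trial was planned around a small or a large symptom difference. The 55% target, which needs no unit, has no planned estimate with an interval. On the planning values at 28 per arm (35 × 0.8), an unadjusted 95% interval around it would run from about 28% to 72%: the standard error of the log ratio is √(0.900²/28 + 0.889²/28) = 0.239, and 0.45 × exp(±1.96 × 0.239) = 0.28 to 0.72.

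Part of this stands. The unit, window and item set are absent from the protocol text, and the placebo pair is not in score-days. The rest does not require a change.

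- The 546 ceiling belongs to this trial's endpoint. The documents do not give the Phase 2a item grading or AUC window. Values from another study that exceed it show that two scales differ, not that the plan contradicts itself.
- Protocol 11.2 labels the values as assumed and names their source. Restating that in terms of coefficients of variation adds no information.
- The sentence in 4.2.1 can fairly mean the same type of endpoint. The protocol openly calls one score 10-point and the other 13-point.
- The spread from 11.5 to 137.5 comes from guessing units and is not a range found in the documents.
- The planned test concerns a difference in means. SAP 3.14.1 already reports the least-squares mean of each group, so the percent reduction can be read off. An interval for the ratio is a reporting preference.
- The SAP contents pass from 3.1 to 3.3 in the public text, so sample-size detail may sit in a part that cannot be seen.

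**Conclusion.** The observation is correct: the planning values have no unit, and the placebo pair cannot lie on the 0 to 546 score-day scale. The effect on the design is nil. Power at 27 per arm is 80.6% whatever the unit, the sample size of about 70 reproduces within rounding, and the primary ANCOVA and its estimates do not use the planning values at all. A statistician reading 11.2 will take them as Phase 2a figures on the Phase 2a scale and use the 55% reduction as the target, which is the sensible reading.

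This rests on both pairs sharing one unit and on the relative effect and relative spread carrying over to the 13-item score. The second assumption is the real risk in the sample size, but it is inherent in planning from a challenge study and the source is disclosed. Naming the unit would help a reader without reducing that risk or altering any result, so no change to the plan is called for.

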11.3 Analysis Populations

The following analysis populations are planned:

- *Safety (SAF) Population*: All subjects who receive at least one dose of study drug. Subjects will be analyzed in the treatment group that corresponds to the study drug received during the study.
- *Modified Intent-to-Treat (mITT) Population*: All subjects who receive at least one dose of study drug. Subjects will be analyzed as treated. The mITT Population is designated as the primary efficacy population.
- *Per Protocol (PP) Population*: All subjects who are randomized and receive all planned doses of study drug and do not have major protocol deviations that may unduly influence outcome. Subjects will be analyzed in the treatment group that corresponds to the study drug received during the study.

- *Pharmacokinetic (PK) Population*: All subjects receiving active study drug and having any measurable plasma concentration of study drug at any timepoint.

11.4 Subject Disposition and Demographic Data

The number of subjects screened, randomized, and in the SAF, mITT, and PK Populations will be summarized using frequencies and percentages. The denominator for the calculation of percentages will be from the number of subjects randomized.

The following categories will also be summarized for subject disposition:

- Completed study drug per the protocol
- Discontinued study drug early and the reason for discontinuation
- Completed the study
- Discontinued from the study early and the reason for discontinuation

Subject demographics will be summarized by treatment group for all subjects in the SAF Population. Appropriate baseline characteristics will be included in addition to demographic characteristics. No statistical testing will be performed.

11.5 Method of Treatment Assignment

Subjects who meet all criteria for enrollment will be randomized to blinded treatment on Day 1 in a 1:1 ratio to 800 mg of EDP-938 or placebo. Assignment to treatment groups will be determined by a computer-generated random sequence using an IWRS. The IWRS will be used to assign investigational product to each subject. To achieve between-group comparability, the randomization will be stratified by asthma/COPD status.

